# Safety Evaluation Set OLEX

The safety evaluation set (SES) of the OLEX period is the subset of all subjects who received study medication (NT 201) at least once during the OLEX period of the study.

If subjects have erroneously been treated with placebo during single OLEX cycles, no safety data in the respective cycle will be displayed. For summaries of safety data of the whole OLEX period or tables displaying changes between single cycles, for example shift tables, all subjects who received placebo in single OLEX cycles will be excluded. In case the OLEX period will be analyzed respective of MP treatment group, the actual treatment in MP will be used for safety data. For efficacy data subjects erroneously treated with placebo during single OLEX cycles will be included. Furthermore, the randomized/ assigned treatment in MP will be used for analysis respective of MP treatment group in chapter 14.1 and 14.2.

In the subject data listings, the treatment group of MP/OLEX will be listed as randomized/ assigned except for the section 16.2.7 and 16.2.8, here the actual treatment group of the respective cycle will be listed. All listings will be sorted by site, treatment group, subject and cycle.

# 6 VARIABLES FOR ANALYSIS

# 6.1 Efficacy Variables

# 6.1.1 Primary efficacy variables

The following variables will be defined as primary and co-primary efficacy variables for the subjects aged 6–17 years:

- Change in mean unstimulated salivary flow rate (uSFR) from baseline (V2) to V3 (Week 4). The mean uSFR is calculated by averaging the two assessments at each visit.
- Global Impression of Change Scale (GICS) at V3 (Week 4) representing the functional improvement in drooling since baseline as assessed by the caregiver/parent(s).

# Unstimulated Salivary Flow Rate (uSFR)

Unstimulated salivary flow rate (uSFR) is measured by the swab method of direct saliva collection.

The saliva collection method by absorbent swabs with safety threads are used instead of cotton rolls to prevent subjects from swallowing the swab. The used swab (made of polyvinyl alcohol (PVA)) has a size of  $35 \times 9 \times 12$  mm, with 15 cm safety thread, provided in double, sterile packaging. It is approved as medical device and used in clinical practice as nasal packs.

Two absorbent swabs (1 swab per side) are placed in the mouth, positioned between cheek and gums directly at the orifices of the salivary ducts of the glands, for 5 minutes. The flow rate can be calculated by the following formula:

Salivary flow rate  $[g/min] = \frac{\text{Weight increase of rolls } [g]}{\text{Time of collection } [min]}$ 

The procedure is repeated after 30 minutes ( $\pm$  5 minutes) and the average of the two results for flow rate is calculated. The assessments are performed under standardized conditions.

## **Global Impression of Change Scale (GICS)**

The Global Impression of Change Scale (GICS) rating is performed by the caregiver before the quantitative measurement of saliva production.

The question of the GICS for the caregiver is: 'Compared to how the child was doing just before the last injection into his/her salivary gland, what is your overall impression of how he/she is functioning now as a result of this treatment?'

The response option for all GICS versions is a common 7-point Likert scale that ranges from -3 = very much worse to +3 = very much improved:

[figure not shown]
#### Table 2: Possible responses on GICS rating

- +2  $\square$  Much improved
- +1  $\square$  Minimally improved
- 0  $\Box$  No change
- -1 🛛 Minimally worse
- -2  $\Box$  Much worse
- -3  $\Box$  Very much worse

# 6.1.2 Secondary efficacy variables

[figure not shown]
The following secondary efficacy variables will be analyzed for the subjects aged 6–17 years:

[figure not shown]
- Change in mean uSFR from baseline (V2) to V4 and V5 (Week 8 and 12, respectively).
- GICS at V4 and V5 (Week 8 and 12, respectively).

Page 14 of 46

CONFIDENTIAL Template: tem-sap-v4.0-20151126 File name: MRZ60201\_3091\_1-sap-final v1.0-2019-06-21.docx Page 16 of 46

# 6.2 Pharmacodynamic Variables

Not applicable

## 6.3 Pharmacokinetic Variables

Not applicable

## 6.4 Pharmacogenetic Variables

Not applicable

## 6.5 Safety Variables

As the analyses of all variables in this study will be shown separately for the two study periods, main period and extension period, the wording "overall and by injection cycle" in the following will be interpreted as "overall (MP and OLEX), per period (MP, OLEX) and by injection cycle" and analyzed as such.

# 6.5.1 Primary safety variable

Occurrence of treatment emergent AEs (TEAEs) overall and by injection cycle.

#### 6.5.2 Secondary safety variables

- Occurrence of treatment emergent AESIs (TEAESIs) overall and by injection cycle.
- Occurrence of treatment emergent SAEs (TESAEs) overall and by injection cycle.
- Occurrence of TEAEs related to treatment as assessed by the investigator overall and by injection cycle.
- Occurrence of TEAEs leading to discontinuation overall and by injection cycle.

#### 6.5.3 Other safety variables

- Occurrence of non-treatment emergent AEs.
- Occurrence of non-serious TEAEs per period.
- Occurrence of TEAEs by worst intensity per period and injection cycle.
- Occurrence of TEAEs by worst causal relationship per period and injection cycle.

- Occurrence of related serious TEAEs per period and injection cycle.
- Occurrence of TEAEs by worst outcome per period and injection cycle.
- Listing of all serious TEAEs of subjects who died per period.
- Listing of TEAEs of standard MedDRA query suicide/self-injury and of TEAEs with possibly suicidal events, per period.
- Vital signs (blood pressure, heart rate, body temperature) at study baseline, V3 (week 4), V6 (week 16), during the main period, at injection visits in the extension period, at end of cycle visits in the extension period and at the end-of-study visit (V18) (Week 64).
- Body height and body mass index (BMI), calculated from body weight and height, at study baseline, final visit of the main period (V6) (Week 16), and end-of-study visit (V18) (Week 64).
- Body weight at study baseline, final visit of the main period (V6) (Week 16), at injection visits in the extension period, at end-of cycle visits in the extension period and end-of-study visit (V18) (Week 64).
- Clinical chemistry (including alkaline phosphatase (AP) and blood glucose (BG)) and hematology at study baseline, final visit of the main period V6 (Week 16), and end-of-study visit V18 (Week 64).
- Occurrence of antibodies against BoNT-A in subjects with  $\geq$  30 kg body weight.
- The number of subjects with suicidal ideation, suicidal behavior, and self-injurious behavior without suicidal intent during treatment based on the Columbia-Suicide Severity Rating Scale (C-SSRS).

#### Columbia-Suicide Severity Rating Scale (C-SSRS)

Prospective monitoring of suicidality with the Columbia-Suicide Severity Rating Scale (C-SSRS) should be considered the most important (but not the only) source of information concerning suicidality.

Suicidality is assessed prospectively in subjects at baseline and every scheduled and unscheduled post-baseline site visit. The appropriate version of this scale ensures the consistent application of this important measure regardless of indication or investigator experience with the subject matter. With C-SSRS in place, administration of this semi-structured clinician-based assessment scale is standardized. The C-SSRS quickly and efficiently identifies those subjects that require additional clinician follow up.

Following versions of the C-SSRS are to be applied only for newly recruited subjects:

- 1. Children's baseline / screening version
- 2. Children's since last visit version.

The C-SSRS interview should only be assessed with children of respective age and cognitive state. Clear age cut-offs for the C-SSRS were not defined by the authors, but it has been found that administration is possible in general for children with a developmental age of about 7 years. Otherwise it should be documented in the electronic Case Report Form (eCRF) that a child was not able to assess the C-SSRS at a respective visit.

At the end of the assessment the subject should not be released from the study center until the results of the C-SSRS (positive or negative) are reviewed and the subject is not considered to be at risk. If there is doubt about whether a subject is at risk, the investigator should obtain appropriate psychiatric consultation.

# 6.6 Other Variables

The following additional variables will be analyzed:

- Subject dispositions (including number of subjects enrolled, number of discontinuations and reason for discontinuations)
- Incidence of protocol deviations
- Demographic data
- Gross Motor Function Classification System (GMFCS) level at baseline (V2) for CP subjects
- Medical history
- Medical history of sialorrhea
- Concomitant diseases
- Previous therapies, including medication and non-drug treatment
- Concomitant therapies, including medication and non-drug treatment
- Injection cycle length, period length and length of entire study period
- Extent of exposure
- Treatment compliance
- Method of administration of the injection

• Use of analgesics and/or sedatives during injection

#### **Gross Motor Function Classification System (GMFCS)**

The GMFCS is a 5-level classification system that is a standardized observational instrument for children with CP developed to measure change in gross motor function over time [Rosenbaum 2002]. It describes the gross motor function of children and adolescents with cerebral palsy (CP) on the basis of their self-initiated movement with particular emphasis on sitting, walking, and mobility. Distinctions between levels are based on functional abilities, the need for aids (e.g., walkers, crutches, and canes) or wheeled mobility, and quality of movement. The original version was developed in 1997 [Palisano 1997]. As of 2007, the expanded and revised version (GMFCS - E&R) further includes an age band for youth 12 to 18 years.

The GMFCS level will be determined at the Baseline Visit (V2)

# 7 STATISTICAL ANALYSIS METHODS

In most cases the end of cycle visit and the injection visit of the following cycle will be performed on the same date. In this case only end of cycle will be documented in the CRF and respective values will also be used for the analysis of the following injection visit. If the visits are not performed on the same date both visits will be documented for most parameters. Only the efficacy variable uSFR will be documented once. This value will be used for the analyses of the end of cycle visit and for the analyses of the injection visit.

# 7.1 Efficacy Variables

All efficacy analyses on data from the main period will be based primarily on the FAS and where deemed sensible additionally, to estimate another estimand, on the PPS. Analyses on data from the extension period are based on the SES only. If not stated otherwise, analyses are performed by all age groups and treatments, i.e. the analyses of the MP will be stratified by "Placebo (6-17 years)", "NT 201 (6-17 years)", "NT 201 (2-5 years)" and "Total NT 201 (2-17 years)". For the OLEX, two sets of tables will be produced: one "respective of main period treatment" showing "NT 201 (MP=Placebo, 6-17 years)", "NT 201 (MP=NT 201, 6-17 years)", "NT 201 (MP=NT 201, 2-5 years)", "NT 201 (MP=NT 201, 2-17 years)" and another set "irrespective of main period treatment" showing "NT 201 (2-17 years)". For the tables respective of main period treatment the randomized/ assigned treatment will be used.

For some variables, analyses by additional age groups and further subgroups will be performed (see Section 7.7.5).

Statistical tests will be two-sided hypothesis tests for between-treatment differences in general. Continuous variables (values and changes from baseline) will be summarized by the number of observed values (n obs), the number of missing or imputed values (n miss/ n imp),

mean, standard deviation, median, quartiles, minimum, and maximum. For qualitative variables, absolute and percent frequencies (n, %) and, if applicable, shift tables will be displayed. Confidence limits and descriptive p-values will be given, where appropriate.

P-values will be reported to four decimal places (e.g. p=0.0375). P-values below 0.0001 will be presented as '<0.0001'.

Mean, standard deviation, Q1, median and Q3 will be reported to one decimal place greater than the data were collected, for derived data an adequate number of decimals has to be chosen. Percentages will be calculated using the denominator of all subjects in a specified population or treatment group. The denominator will be specified in a footnote to the tables for clarification if necessary. Percentages will be reported to one decimal place.

In general values measured at the baseline injection visit (V2) will be used as study baseline value. If data is missing for this visit the last valid value before first injection will be used instead. If e.g. the uSFR is not measured at Visit 2 (Baseline) and the last valid value before first injection is the uSFR value at screening then this value will be used as study baseline value in all analyses described below.

For all MP and OLEX tables the treatment groups will be analyzed as randomized/ assigned in the respective study period. For all OLEX tables, which are stratified by visit/cycle, only subjects with injection in the respective cycle are included; for the end-of-study visit all subjects with at least one injection in the OLEX are included (irrespective of regular or premature discontinuation). Additional to "End of Study" visit "Cycle 4 Week 16" visit will be analyzed. For "Cycle 4 Week 16" only subjects regularly completing cycle 4 are included. In general, percentages will be based on all subjects treated in the respective cycle.

# 7.1.1 Primary/Co-primary Efficacy Variable

The main co-primary estimands will be defined as follows:

Objective	Evaluate whether treatment with NT 201 is superior to treatment with placebo with respect to reducing sialorrhea
Population	Subjects treated
Variable(s)	uSFR and GICS, evaluated at 4 weeks after treatment in comparison to baseline
Handling of intercurrent events	To be defined during the BDRM
Population-level summary of the variable(s)	Difference in mean uSFR change from baseline to week 4 / mean GICS at week 4 between NT 201 and placebo

The main analytic approach or primary confirmatory analysis of the co-primary estimands will be a mixed model repeated measurement analysis (MMRM, 2-sided, significance level alpha=0.05) with comparison of least square means between NT 201 and placebo performed on the group of subjects within the FAS aged 6-17 years.

The dependent variables will be the change in uSFR from baseline (V2) to V3 (Week 4) ( $\Delta$ uSFR) and the carer's/parent's GICS at V3 (Week 4), respectively.

The independent variables are defined as treatment group, pooled investigation sites (see section 7.7.6) and age groups (6-9 years, 10-12 years and 13-17 years) as fixed factors, visit\*treatment as interaction term, and visit as repeated factor. To adjust for the baseline status, the MMRM of the uSFR change additionally includes the baseline score of the uSFR as covariate. Since no baseline assessment of the GICS is available, the baseline mTDS rated by the parent(s)/carer is used as covariate in the MMRM model for the GICS.

The following SAS code will be used:

```
proc mixed data = dataset;
  class treatment pooled_site age_group subject visit;
  model AuSFR (GICS) = treatment pooled_site age_group uSFR_baseline
        (mTDS) visit visit*treatment /solution ddfm=kr;
  repeated visit / subject = subject type = un grp = treatment
  LSMeans visit*treatment pooled_site age_group / pdiff CL alpha =
0.05;
run;
```

where:	treatment	= treatment group (NT 201 (6-17 years) and Placebo (6-17 years))
	pooled_site	= pooled investigation sites
	age_group	= age group (6-9 years, 10-12 years and 13-17 years)
	uSFR_baseline	= Value of uSFR at Visit 2 (Baseline)
	mTDS	= Value of mTDS at Visit 2 (Baseline)

Only if both co-primary efficacy variables show a statistically significant difference compared to placebo the superiority of NT 201 over placebo will be considered to be proven. Therefore, no  $\alpha$ -adjustment for multiple testing is necessary.

Intercurrent events with potential bias on the co-primary endpoints will be identified prior to or during the BDRM. In case these events are judged as relevantly biasing the co-primary endpoints, conservative sensitivity analyses on the MMRM model will be specified during the BDRM.

In addition to the MMRM, an analysis of covariance (ANCOVA) model will be performed on the FAS (age 6-17 years) using observed cases as well as using the baseline observation carried forward approach (BOCF, no effect) for uSFR and imputing missing GICS entries as "no change". The ANCOVA models will be performed by use of the following SAS code:

```
proc mixed data = dataset;
  class treatment pooled_site age_group;
  model AuSFR (GICS) = treatment pooled_site age_group uSFR_baseline
        (mTDS)/solution ddfm=kr;
  LSMeans treatment pooled_site age_group / pdiff CL alpha = 0.05;
  where visit = V3;
run;
```

Furthermore, a non-parametric Wilcoxon rank-sum test will be performed as sensitivity analysis of the co-primary efficacy variables to investigate the impact of potential deviations from the assumption of normal distribution. The test will be performed for FAS (age 6-17 years) using observed cases as well as using BOCF for uSFR and "no change" for GICS. The Wilcoxon rank-sum test will be performed by use of the following SAS code:

```
proc npar1way data=dataset wilcoxon;
  class treatment;
  var ΔuSFR;
run;
```

For the GICS, a logistic regression will be performed as sensitivity analysis to the distribution assumption. The responder rate will be determined, i.e. all subjects with GICS entry of at least +1 (Minimally improved).

Treatment arm comparisons with respect to responders based on the GICS entries will be performed analogously to the primary efficacy analysis, but based on estimates of logistic regression models. The dependent variable of these models will be the response to treatment. Treatment group, pooled investigation site and age group will be included as factors into the models. Baseline adjustment will be done by including the baseline values of the mTDS as covariate. The following SAS code will be used for estimation:

```
proc logistic data=dataset desc order=formatted;
    class treatment pooled_site age_group;
    model resp(GICS) = treatment pooled_site age_group mTDS;
    where visit = V3;
run;
```

The comparison with respect to treatment group will be performed by use of the Odds Ratios and their corresponding 95% Wald confidence intervals (CI).

This analysis will be performed on the FAS (6-17 years) without imputation of missing values and by imputing subjects with missing GICS entries as non-responder. In the observed case analysis, percentages will be based on subjects with values at the respective visit. When using the imputation approach, percentages will be based on all subjects with observed or imputed values at the respective visit. For the response rate frequencies, including 95% confidence limits and descriptive p-values for NT201 (6-17 years) vs. placebo (6-17 years) (based on Fisher's exact test or or  $\chi^2$ -test as appropriate as appropriate) will be given. If one of the logistic regression models is not estimable due to a too small amount of responders or non-responders, this analysis will be replaced by descriptive summary statistics.

In addition, descriptive summary statistics and frequency tables (for GICS only) of values and changes from baseline (uSFR only) will be given for the primary and co-primary efficacy variables overall and by age groups and further subgroups (observed case and imputed values). A frequency table will also be given for the GICS responder/non-responder.

All analyses stated above will also be performed on the PPS. This addresses a different estimand, namely:

[figure not shown]
Objective	Evaluate whether treatment with NT 201 is superior to treatment with placebo with respect to reducing sialorrhea when applied as specified in the protocol	
Population	Subjects who are treated and follow the procedures in the protocol related to the treatment or the observation of its effect (i.e. e.g. do not take prohibited medication)	
Variable(s)	uSFR and GICS, evaluated at 4 weeks after treatment in comparison to baseline	
Handling of intercurrent events	To be defined during the BDRM	
Population-level summary of the variable(s)	Difference in mean uSFR change from baseline to week 4 / mean GICS at week 4 between NT 201 and placebo	

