# 8.2.1 *Methods of assigning subjects to treatment groups*

Each subject screened will be given a screening number through the IWRS. Rescreened subjects will receive a new screening number. Only the subjects who are randomized will receive a randomization number at baseline visit (V2).

Randomization to NT 201 and placebo in a ratio of 2:1 will be applied during the main period, for the subjects aged 6–17 years. Subjects aged 2–5 years will not be randomized.

Randomization will include staggering of the age groups as described in Section 6.3.

The randomization officer responsible will perform the random allocation of treatments to subjects using the computerized randomization program

Merz Pharmaceuticals GmbH MRZ60201 3091 1

, Germany) by preparing a randomization list for each age group including – for each subject – a randomization number and the allocation to treatment for the main period. The IWRS will allocate the randomization number to a subject and will determine a medication kit with a unique medication number for each injection visit of the subject. The randomization number and the medication numbers for each subject will be recorded in the eCRF.

Recruitment in each age group will be closed when the requisite number of subjects has been recruited; for details see Section 6.3. Slight over-recruitment (up to 10%) may occur in consequence of technical factors. After the end of recruitment, subjects leaving the study prematurely will not be replaced.

The randomization list will be sealed and locked in the sponsor's quality management department and will not be accessible before database closure.

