# **3 CLINICAL STUDY DESIGN AND OBJECTIVES**

# 3.1 Clinical Study Design

This is a prospective, randomized, double-blind, placebo-controlled, parallel-group, multicenter study with a screening period, a main period (MP) followed by an open-label extension (OLEX) period.

Subjects (adolescents and children) are recruited in a staggered manner in consecutive age groups: 10–17 years (inclusive), 6–9 years (inclusive) and 2–5 years (inclusive). In the main period the subjects in the age groups from 6 to 17 years are randomized to receive doubleblind, placebo-controlled treatment. Subjects aged 2–5 years at screening are not randomized, but are treated with NT 201 in an open-label fashion. In the extension period all subjects are treated with NT 201 in an open-label fashion.

The study consists of four injection cycles. The first injection cycle is the main period. The total duration of the main period is 15–22 weeks (comprising the screening period of up to 4 weeks before the first injection and the main treatment period of  $16 \pm 2$  weeks). This first injection cycle is followed by three subsequent open-label injection cycles ( $16 \pm 2$  weeks each) for all subjects. The total treatment period thus lasts for 56–72 weeks after the first injection for those completing all four injection cycles. For the safety of subjects, a Data Monitoring Committee (DMC) assesses adverse events (AEs), including adverse events of

special interest (AESIs) and serious adverse events (SAEs) at regular intervals and after each group of 30 subjects has been fully recruited.

The treatment comprises four injections of NT 201 (parotid and submandibular glands, bilaterally); the dose is defined according to body weight (approximately 2 U/kg). At the end of the main period, subjects are assessed for eligibility to enter the extension period.

There will be one final analysis at the end of the study including MP and OLEX.

The study includes the following visits:

Table 1: Visit Schedule

Screening Visit (V1):	Day -28 to -7
-----------------------	---------------

Placebo-controlled main period (first injection cycle):

Baseline injection visit (V2):	Day 1 of first injection cycle, randomization
Assessment visit (V3):	Week $4 \pm 3$ days
Assessment visit (V4):	Week $8 \pm 7$ days
Assessment visit (V5):	Week $12 \pm 7$ days
Final visit of main period (V6):	Week $16 \pm 2$ weeks

**Open-label extension period** (second, third and fourth injection cycle):

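### The Wilcoxon sensitivity test is fully unadjusted: it ignores the randomization age groups as well as site and baseline, so a disagreement with the models could not be put down to non-normality alone

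*SAP*

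**What the plan says.** SAP 7.1.1 states that "a non-parametric Wilcoxon rank-sum test will be performed as sensitivity analysis of the co-primary efficacy variables". Its stated purpose is "to investigate the impact of potential deviations from the assumption of normal distribution". The code is "proc npar1way data=dataset wilcoxon" with treatment as the only class variable, and there are no strata and no covariates. The test is run on observed cases and again with missing uSFR set to baseline and missing GICS set to no change. It is repeated on the PPS and, under SAP 7.1.2, at the later main-period visits.

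The other analyses in the same section keep the design and prognostic terms. The MMRM has pooled site and "age groups (6-9 years, 10-12 years and 13-17 years) as fixed factors", and "the MMRM of the uSFR change additionally includes the baseline score of the uSFR as covariate" (baseline mTDS for GICS). The Week 4 ANCOVAs use the same terms without the repeated visits. For the GICS logistic regression, "Treatment group, pooled investigation site and age group will be included as factors into the models", with baseline mTDS as covariate.

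On the design side, SAP 3.1 says that subjects "are recruited in a staggered manner in consecutive age groups". Protocol 6.3 shows that only the 10–17 and 6–9 year groups are randomized, and Protocol 8.2.1 describes "preparing a randomization list for each age group". Age group is therefore a randomization stratum.

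**The concern.** A check on one assumption is most useful when the rest of the analysis stays the same. Here the check on normality also removes every adjustment. Suppose the MMRM is significant and the Wilcoxon test is not. The cause could be the shape of the data, lost stratification, lost baseline or site adjustment, or different use of the visits, and the plan gives no way to tell these apart.

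This weighs more on uSFR change than on GICS. Both co-primaries must succeed. GICS has a second, adjusted distribution check in the logistic regression. For uSFR change the Wilcoxon test is the only non-normality check.

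Age could plausibly matter. Protocol 4.1.1 says that pre-pubertal children secrete less saliva, and it cites a study in which drooling fell with dental age. Both statements concern levels, not change after treatment, so the size of any age effect on the endpoints is unknown.

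**Working it through.** **Plan's own figure.** Inputs from SAP 4 and 4.2: 146 v 73, difference 1.0, SD 1.93, two-sided 5%. SE = 1.93 × √(1/146 + 1/73) = 0.277, and 1.0/0.277 = 3.61. Power ≈ Φ(3.61 − 1.96) = 95.1% (94.9% by noncentral t). The stated 95% reproduces. The documents state no power for the Wilcoxon test.

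**What each analysis keeps.**

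| Analysis | Age group | Pooled site | Baseline | Repeated visits |
|---|---|---|---|---|
| MMRM | yes | yes | yes | yes |
| ANCOVA at Week 4 | yes | yes | yes | no |
| Logistic regression (GICS) | yes | yes | yes (mTDS) | no |
| Wilcoxon | no | no | no | no |

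**Cost of ignoring age: 7-point score.** Assumptions: strata of 141 and 78, exact 2:1 allocation in each, normal latent score rounded to −3..+3, and an age effect expressed in within-stratum SD. The standardized treatment effect is 1.0/1.93 = 0.52.

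An age effect *a* adds a²·f(1−f) to a within-stratum variance of 1, with f = 78/219 and f(1−f) = 0.229. As a share of total variance this is 0.0143/1.0143 = 1.4% at 0.25 SD, 0.0573/1.0573 = 5.4% at 0.5 SD and 0.229/1.229 = 18.7% at 1.0 SD.

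Power from 8,000 simulated trials:

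| Age effect | Plain Wilcoxon | van Elteren | Difference |
|---|---|---|---|
| 0 | 92.3% | 92.3% | 0 |
| 0.25 SD | 91.9% | 92.2% | 0.3 |
| 0.5 SD | 91.7% | 92.3% | 0.6 |
| 1.0 SD | 88.5% | 92.1% | 3.6 |

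A separate run of 4,000 trials gave a gain of about 3 points at 1.0 SD.

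**Type I error.** For the plain test it was 4.9% at 0.5 SD and 3.0% at 1.0 SD. The reason is that allocation is balanced within strata, so age adds nothing to the real variability of the test statistic, while the unstratified null variance still counts it. The test errs towards non-significance.

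**Skewed or heavy-tailed data.** The loss is larger but depends heavily on the assumed shape and effect.
- Lognormal (sigma 0.8), treatment effect 0.25 SD, same strata, plain v stratified power: 86 v 86% with no age effect, 75 v 86% at 0.5 SD, 59 v 86% at 1.0 SD. Type I error of the plain test: 5.0, 3.6 and 1.5%.
- Equal strata, difference 0.7, total SD 1.93, 3,000 runs. With age explaining 5% of variance: lognormal (sigma 0.75) 96.0 v 98.0%, t with 3 df 91.5 v 93.6%. With age explaining 10%: 95.2 v 98.7% and 90.3 v 94.8%.

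**Age is not necessarily the largest omission.** Adjusting for a baseline that explains a share R² of the variance multiplies the SD by √(1−R²). At R² = 25% (assumed), the SE is 0.277 × 0.866 = 0.240 and t-test power is 98.7%. At 50% (assumed), the SE is 0.277 × 0.707 = 0.196 and power is 99.9%. Both compare with 95.1% unadjusted.

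**The case against.** The strongest reply is that nothing rides on this test. SAP 7.7.4 makes every result outside the two co-primary MMRM tests descriptive, and success depends on those two alone. An unadjusted rank test beside adjusted models is an ordinary choice. GICS already has the adjusted logistic regression. The observed-case and BOCF ANCOVAs at Week 4 use the same data as the Wilcoxon test, so comparing them removes the repeated-visit difference. All of this stands, and it limits the point to an optional improvement.

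A reader might go further than the documents allow in three ways.
- **That the test is underpowered.** No power target is set for it, no age effect is given, and the loss on a 7-point score is under 1 point unless the age effect is large.
- **That ignoring the strata makes the test invalid.** In the simulations its type I error is at or below the nominal level, so the risk is a missed signal and not a false one.
- **That stratifying by age would isolate non-normality.** It would not, because site and baseline would still be missing, and baseline may matter more than age.

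What survives is narrower. The test changes several things at once, uSFR change has no other non-normality check, and stratifying costs essentially no power when age has no effect.

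**Conclusion.** The Wilcoxon test is valid but fully unadjusted, so a disagreement with the MMRM or ANCOVA could not be attributed to non-normality alone. When age is prognostic the test is also conservative. At the plan's effect on a 7-point score the power lost is under 1 point for age effects up to 0.5 SD and about 3 to 4 points at 1.0 SD. In the skewed and heavy-tailed settings examined it ranges from about 2 points to 11 points when age explains about 5% of variance, depending on the assumed distribution and treatment effect.

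These sizes rest on assumed age effects, an assumed split of the 219 subjects, and exact 2:1 allocation within each age list. The documents give no age effect and no planned split. The primary conclusion is unaffected, and the point is a minor improvement to a descriptive sensitivity analysis.

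**What to change.** Next to the plain Wilcoxon test, add a van Elteren test stratified by the randomization age groups (6–9 and 10–17). Run it for observed cases and with BOCF / no-change imputation, for both uSFR change and GICS at Week 4. Name the strata in the SAP, because the MMRM uses a finer split (6–9, 10–12, 13–17).

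State that the rank tests will be read against the ANCOVA on the same data (observed-case with observed-case, imputed with imputed). Any remaining difference then reflects distribution plus the unadjusted baseline and site terms. If a closer match is wanted, a rank-based ANCOVA that keeps the model covariates would go further.

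While editing the code block, add GICS and the Week 4 restriction. The printed code names only uSFR change and lacks the visit condition that the ANCOVA code has.

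The cost is a stratified version of one procedure call and a few lines of SAP text. No extra data are needed and the confirmatory analysis does not change.
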